7. SPECIMEN AND DATA COLLECTION

7.a. Blood We will obtain 10-hour fasting blood samples at the beginning and at the end of each intervention period. The first sample will be sent to QUEST Diagnostics (a CLIA certified lab) for clinical chemistries (to confirm eligibility; see Section 6 for specifics). Participants will come to the Prevention Center at the Fred Hutch where certified personnel will collect four 10-ml vacutainers of blood; for plasma and serum. Specimens will be stored at -80°C.

7.b. Stool samples at three timepoints in each intervention arm, beginning, middle and end; for : a) exfoliated colonocyte transcriptome (mRNA) analysis, and b) fecal microbiome analyses. Participants

will collect small samples of stool into vials we provide that are pre-filled with RNAlater for microbial DNA,⁵⁹ RNAsheild for exfoliated colonocyte transcriptomics,⁶⁰ and in 95% ethanol for SCFA and future metabolomics measures.⁶¹ Human transcriptome profiles are stable for at least 60 h at 4°C prior to addition of RNAsheild solution and once RNAsheild solution is added, at -80°C for at least 2 yrs.^{48, 60}

7.c. Questionnaires: Dietary Assessment We will use an established, validated food frequency questionnaire (FFQ) to characterize food and nutrient intakes of the study participants over the 3 months prior to baseline to characterize habitual diets (typically low in n-3 PUFA and fiber and high in n-6 PUFA). **Health and Demographics** will also be collected. A **General Symptoms and Bowel Habits Questionnaire** will also be provided every time participants collect stool- this is a useful tool to determine intervention effects.

8. LABORATORY PROCEDURES

8.a. Plasma n-3 PUFA Assays To confirm adherence to n-3 PUFA exposure, we will isolate total phospholipids from plasma collected on days 0 and 30, trans-esterify, and measure EPA and DHA by GC/MS.⁶² This work will be performed by our Co-Investigator [name] at Texas A&M.

8.b. Host Gene Expression Using RNA-Seq Poly A⁺ RNA will be isolated for exfoliated cells in stool as we describe.^{48, 60, 63} An Agilent 2100 Bioanalyzer will be used to assess integrity of fecal poly A⁺ RNA as we described.^{64, 65} This work will be performed by MPI, [name] at Texas A&M.

8.c. Fecal Microbiome Analysis Using ddPCR We will extract genomic DNA from stool samples and use the QX200 ddPCR system (Bio-Rad) to quantify bacterial genes from the two major butyrate synthetic pathways, butyryl-CoA:acetate CoA-transferase (*but*) and butyrate kinase (*buk*) and total bacterial load (16S rRNA genes) according to the manufacturer's instructions, and primer and probe set optimized for the selected genes.⁶⁶⁻⁷⁰ We have chosen this assay because it is more reliable, accurate, precise, and less prone to inhibition than qPCR. Butyrogenic potential of the microbiome will be defined as \sum (butyryl-CoA:acetate CoA-transferase (*but*) + butyrate kinase (*buk*) genes)/(total bacterial load 16S rRNA gene).⁶⁶⁻⁶⁹ This work will be performed in the [name] lab at Fred Hutch.

9. DATA ANALYSIS

9.a. Data entry and quality assurance procedures. We will code and enter data from questionnaires, tracking forms, etc., and integrate with laboratory data, and monitor adherence to protocols for data entry, sample processing, storage, and analysis.

9.b. Aims testing, Overview: In **Aims 1 and 2** our analyses will investigate the response to the fiber and n-3 PUFA intervention at levels of **a) individual genes or variables** and **b) pathways and networks.** At the individual marker level (a) we will test genes and the butyrogenic potential (Aim 1 and 2) for differences due to intervention using univariate models, adjusting for appropriate covariates. At the pathway/network level (b), analysis will focus on hypothesized CRC pathways and employ gene-set ("global") enrichment analysis tests to evaluate changes in host gene pathways (Aim 1). When prior genetic/metabolic network structure is known within a pathway, the analysis will account for this.

Models: **a)** For single-gene/variable analyses (Aims 1 and 2), we use linear mixed models with a random effect for participant to account for the repeated measures of marker y during and at the end of each intervention. Fixed effects will include an indicator, *I*, for intervention as well as demographic covariates (e.g., age, sex, BMI) which will be tested by randomization and included where appropriate. Although randomization to intervention sequence should alleviate the potential for *differential* carryover effects between periods, models will include an indicator *S* of randomization sequence. Error terms ϵ_{ik} are assumed to be correlated within, and independent between, participants. In summary, models take the form $y_{ik} = \alpha_i + I_{ik} + S_i + \epsilon_{ik}$, where α_i is a random effect for subject. Robust standard errors will be used to test for differential effect of intervention, and all p values will be corrected for multiple testing by controlling the FDR using Benjamini-Hochberg⁷¹. **b)** For pathways, we will apply kernel association testing (KAT) procedures.^{72, 73} These multivariate methods allow for pathway-wide testing and modeling in a manner which extends gene-set style tests. They incorporate adjustment for covariates and generalize tools such as the globalTest,⁷⁴ used in genomics studies, and PERMANOVA,⁷⁵⁻⁷⁷ common to microbiome analyses. Network or structural relationships (e.g., metabolic) between genes in a pathway

are easily incorporated into construction of a similarity/kernel matrix on which KATs are based^{72, 78}. These known (or estimated) interactions can enhance the KAT testing procedure to increase power.^{79, 80} Similar methods analyzing gene-gene networks have been successful in crossover dietary studies.⁸¹ We will account for the repeated-measures aspect of the crossover design in these models by applying a variant of family-based KAT.^{82, 83} Finally, longitudinal data collected on days 0, 15, and 30 of each period will be analyzed using a linear mixed model for each measure, as above. Terms for time and effect modification by intervention (time*intervention) will be added to this model if the data support autocorrelation within a measure across time. For longitudinal analyses of multivariate data (i.e., pathways/ gene-sets), we will test for longitudinal differences due to intervention by way of a repeated-measures KAT^{82, 83} and a variant of GSA.⁸⁴ We will consider effects of butyrogenic potential (defined as above and below the median; **Aim 2**) on host gene expression responses (**Aim 1**).

9.c. Power and sample size. This is a randomized, controlled crossover pilot feasibility study in 30 healthy men and women, designed to generate preliminary data to inform a larger human mechanistic study. Based on our previous experience, we are confident we will detect gene expression changes with the fiber + n-3 PUFA intervention. **Aim 1:** In our FlaxFx study³² with a similar crossover design, we detected differential expression of 32 genes between placebo and lignan extract (FDR<0.05) in exfoliated cells (n=42 participants). Given the impact of dietary fiber on multiple pathways in animal models,⁸⁵ we anticipate similar or better power in the current study. In addition, we also considered power for single-gene analysis in this crossover study (n=30). Using a 2-sided paired t-test at significance level alpha=0.05 and a range of effect sizes, conservative estimates are: power of at least 80% for effect sizes larger than 0.5. **Aim 2:** a power estimate for ddPCR data, based on differences in *but* gene abundance with low- ($4.96 \times 10^{11} \pm 3.22 \times 10^{10}$ copies/g feces) and high-fiber diets ($1.37 \times 10^{12} \pm 1.47 \times 10^{11}$) in healthy individuals (n=30),⁸⁶ at significance level alpha=0.05 and effect sizes larger than 0.8 , we estimate power at least 95 % to detect diet-related differences in this gene. We anticipate a similar distribution for *buk*.

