4. STUDY DESIGN

The study is designed as a randomized, cross-over, placebo-controlled dietary intervention of supplemental soluble fiber and supplemental n-3 PUFA compared to corn oil and maltodextrin control. We will randomize participants to one of the two treatment orders, either supplemental fiber and fat first followed by the placebo in the second period or the placebo first followed by supplemental fiber and fat. Each treatment will be 30 days in duration with at least a 60-day washout period between treatments. Stool samples will be collected at the beginning, middle (day 15) and end of each of the two 30-day intervention periods.

It will take participants at least 4 months to complete the trial. Details of the activities and timeline:

Activity	1-2 weeks before Day 0	DAYS in Period 1					at least 2 months (washout)	DAYS in Period 2				
		0	1 - 14	15	15 - 29	30		0	1 - 14	15	15 - 29	30
Info session and consent	1											
Fasting morning blood draw*	2							6				
Collect stool												
Deliver stool & get study supplements		3						6				
Take study supplements daily												
Collect stool												
Deliver stool & get study supplements				4						7		
Take study supplements daily												
Collect stool												
Fasting morning blood draw & deliver stool						5						8

*Visit 2: If results from liver/kidney functions test are abnormal, participant will not continue with study

Study Visit # = visits to Fred Hutch
= activities at home

4.a. Fiber and Fat Supplements The active treatment period will include supplemental soluble fiber (35 g/d) + supplemental n-3 PUFA (6 g/d EPA+DHA).

Supplemental Fiber: The soluble fiber with known fermentation profiles will be provided by Tate & Lyle, a well-established food and beverage ingredient company. For placebo, we will use maltodextrin provided in the same packaging and by the same company.

Supplemental n-3 PUFA: We will use a commercial fish oil supplement (Omega Cure, Omega3 Innovations), consumed as 2 vials daily. Each vial (11.75 g oil) delivers 3 g EPA +DHA in a 1:1 ratio. For placebo, we will use equivalent amounts of corn oil in visually identical packaging provided and by the same company.

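### The single-gene model leaves out the day-0 stool value, the longitudinal model may let it dilute the effect, and the sequence term does not protect the estimate from carryover

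*Combined protocol and SAP*

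**What the plan says.** Section 4 (Study Design) states: "Stool samples will be collected at the beginning, middle (day 15) and end of each of the two 30-day intervention periods". The visit table there has participants hand in the day-0 stool at the visit where they receive that period's supplements, so day 0 precedes treatment in each period.

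Section 9.b, Models (a), covers "repeated measures of marker y during and at the end of each intervention". The model is y = α + I + S + ε, "where α_i is a random effect for subject". The other covariates named are "demographic covariates (e.g., age, sex, BMI) which will be tested by randomization and included where appropriate". No day-0 value appears.

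On carryover, the same paragraph opens "Although randomization to intervention sequence should alleviate the potential for" differential carryover and continues that "models will include an indicator *S* of randomization sequence". Section 4.c gives the 60-day washout and its rationale.

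Later in Section 9.b, "longitudinal data collected on days 0, 15, and 30 of each period will be analyzed using a linear mixed model for each measure, as above". Time and time-by-intervention terms join that model only if the data support autocorrelation. No day-0 comparison between sequences is specified.

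**The concern.** The trial collects a pre-treatment sample in each period, and the plan gives it neither of its two natural uses.

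First, the random participant effect removes a person's stable level but not drift between periods that start at least 90 days apart (30 days of treatment plus 60 of washout). The period-specific day-0 value can carry information on that drift. In the longitudinal model, day 0 is instead one of three outcomes. Whether its lack of a treatment effect is modelled depends on autocorrelation, which concerns error structure and says nothing about whether the effect varies with time.

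Second, S is offered in the sentence on carryover, but it is constant within a participant while the intervention contrast is made within participants. A reader could think carryover has been dealt with in the model when it has not.

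**Working it through.** **1. The plan's own power figure.** Section 9.c uses a two-sided paired t-test, alpha 0.05, n=30, and states at least 80% power for effect sizes larger than 0.5. At exactly 0.5, the normal approximation gives Φ(0.5·√30 − 1.96) = 78.2%. The exact noncentral t gives 75.4%, and 80% needs an effect size of 0.529. I use 75.4% as the unadjusted reference.

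**2. Day 0 as an outcome without time-by-intervention.** Suppose the effect is 0 at day 0 and D at days 15 and 30. With I alone, the model averages the three days: (0 + D + D)/3 = 2D/3. For power, assume unit variances, within-period correlation rw and between-period correlation rb. Neither is in the documents.
- Variance of the between-period difference: 2[(1+rw)/2 − rb] for the mean of days 15 and 30, and 2[(1+2rw)/3 − rb] for the mean of all three days.
- Set D so that the mean of days 15 and 30 has effect size 0.5 (power 75.4%).
- At rw = rb = 0.4: D = 0.5·√0.6 = 0.387. The diluted effect size is (2/3)(0.387)/√0.4 = 0.408, power 58%.
- At rw 0.6, rb 0.4: D = 0.5·√0.8 = 0.447. The diluted effect size is (2/3)(0.447)/√0.667 = 0.365, power 49%.

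**3. What S does.** Let carryover c from active reach the following placebo period. The active-minus-placebo difference is effect − c in the active-first sequence and effect in the other. With equal sequences, the mean is effect − c/2. S is orthogonal to the within-person contrast when every participant has both periods complete. I simulated 30 participants, two samples per period, effect 0.5 and c = 0.3. The mean estimate was 0.35 (= 0.5 − 0.15), and the estimates with and without S differed by less than 1e-15 in every run.

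**4. Day 0 as a covariate.** Let D̂ be the between-period difference in the mean of days 15 and 30, and d0 the same difference at day 0.
- Var(D̂) = 2[(1+rw)/2 − rb]; Var(d0) = 2(1 − rb); Cov = 2(rw − rb); R² = Cov²/[Var(D̂)·Var(d0)].
- Cost of estimating one covariate at n=30: a factor of about 1 + 1/27 = 1.04.
- Example, rw 0.5, rb 0.3: R² = 0.4²/(0.9 × 1.4) = 0.127. The net variance ratio is 0.873 × 1.037 = 0.91.

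| rw / rb (assumed) | Variance ratio before cost | Net variance ratio | Power, effect size 0.5, n=30 |
|---|---|---|---|
| no covariate | – | 1.00 | 75% |
| rw = rb | 1.00 | 1.04 | 74% |
| 0.4 / 0.3 | 0.96 | 1.00 | 75% |
| 0.5 / 0.3 | 0.87 | 0.91 | 79% |
| 0.6 / 0.4 | 0.83 | 0.86 | 81% |
| 0.7 / 0.4 | 0.67 | 0.69 | 89% |

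These powers are at unadjusted alpha 0.05, as in Section 9.c, not after the planned FDR control.

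**5. Raw change from day 0.** Its variance ratio is [Var(D̂) + Var(d0) − 2Cov]/Var(D̂). At 0.5/0.3 this is (0.9 + 1.4 − 0.8)/0.9 = 1.67, a loss.

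**6. Limits of the remedy.** If carryover c is present at period-2 day 0 but gone by day 15, the unadjusted contrast is unbiased and the adjusted one shifts by slope × c/2, where slope = (rw − rb)/(1 − rb). That is 0.286c/2 = 0.14c at 0.5/0.3 and 0.333c/2 = 0.17c at 0.6/0.4. Comparing period-2 day-0 values between about 15 and 15 participants has 26% power at a standardized difference of 0.5 and 56% at 0.8, at alpha 0.05 before any FDR control.

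**The case against.** Three stronger readings are tempting, and the documents do not support them.

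- A reader might infer that the day-0 samples are discarded. They are not: Section 9.b puts them in a mixed model for each measure and plans repeated-measures tests for gene sets.
- A reader might infer that day-0 stool is the only direct check on carryover, or that the plan rests on S alone. The main safeguard is the 60-day washout, justified in Section 4.c by 45-day clearance of blood DHA+EPA and by rapid epithelial and microbial turnover. Section 8.a also measures plasma EPA and DHA on days 0 and 30, which would show residual n-3 exposure. That assay is planned for adherence, however, and cannot show residual expression or fiber effects. The plan does not claim outright that S removes carryover; the sentence only invites that reading.
- A reader might infer that adjustment sharpens every gene-level contrast. Under the exchangeable correlation implied by a single participant effect, it gains nothing and costs about 4%. The correlations will differ by gene.

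It is also fair to say that a randomized crossover contrast needs no baseline adjustment to be valid in the absence of carryover, and that this is a pilot. That limits the precision argument. It does not answer the dilution to two thirds or the lack of effect of S, neither of which depends on an assumed correlation.

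**Conclusion.** The point stands in a limited form. Model (a) omits a baseline that the trial already collects. The longitudinal model can shrink a real effect to two thirds if its time terms are left out; this assumes no effect at day 0 and a constant effect at days 15 and 30. S gives the intervention estimate no protection against carryover when participants have complete data; the bias is minus half the carryover with equal sequences.

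The precision argument is conditional. Net variance changes run from about a 4% loss (rw = rb) to about a 31% gain (0.7/0.4). A within-period correlation above the between-period one is plausible, because same-period samples are 15 to 30 days apart while the periods start at least 90 days apart. The documents do not establish it. Nothing here shows that carryover is present, or that the 60-day washout is inadequate.

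**What to change.** 1. In model (a), add the within-person difference in day-0 values between periods as a covariate. Do not analyse raw change from day 0.
2. In the longitudinal model of days 0, 15 and 30, include time and time-by-intervention unconditionally, and report the intervention contrasts at days 15 and 30. Constraining day-0 means to be equal across treatments would assume the absence of carryover, so that version should not double as the carryover check.
3. Report period-2 day-0 expression and butyrogenic potential by sequence, alongside day-0 plasma EPA and DHA. Label this descriptive, state its low power (about 15 per sequence), and attach no decision rule; a null result would not exclude carryover.
4. Reword the sentence on S so that it is not presented as handling carryover.

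The cost is SAP wording and modest analysis time, with no new samples. The downsides are up to about 4% more variance for genes whose day-0 values are uninformative, and a shift of about 0.14 to 0.17 times the carryover (at 0.5/0.3 to 0.6/0.4) if carryover is present at period-2 day 0 but gone by day 15. Reporting the unadjusted estimate beside the adjusted one would show how much either matters.

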1. PROTOCOL SYNOPSIS

Studies in animals have shown that both long-chain n-3 polyunsaturated fatty acids (PUFA) and a bacterial metabolite of dietary fiber (butyrate) may reduce colon tumor formation, and that the two in combination are even more effective than either alone. Several different mechanisms of action have been suggested. In humans, some epidemiologic studies suggest that people who consume high-fiber diets or use n-3 PUFA supplements may have a lower risk of colorectal cancer, but there are currently no controlled dietary interventions evaluating the combined effects of these two dietary constituents on colorectal cancer risk factors in humans. We will test the combination of n-3 PUFA and fiber on gene expression in colon cells that are part of the pathways important to cancer risk and will seek to understand how variation in the gut bacterial community may affect response to intervention.

Design: A randomized, placebo-controlled, double blinded, crossover dietary intervention

Sample Size: Recruitment of 40 participants with the goal of having 30 complete study measures.

Participants: Men and women

Selection: Individuals from the Greater Seattle area who are normal to overweight (BMI of 18-30 kg/m²) and between the ages of 50-75, who typically consume diets with 20g fiber or less per day. We will recruit U.S. racial minorities at an overall level of 32%, which mirrors the minority distribution in Seattle/King County

Exclusion: The exclusion criteria will address a mix of medical and practical issues: 1) chronic medical illness, history of gastrointestinal disorders (e.g., ulcerative colitis, Crohn disease, celiac sprue, HNPCC, familial adenomatous polyposis, pancreatic disease, previous gastrointestinal resection, radiation or chemotherapy, and cancer (other than non-melanoma skin cancer); 2) weight change greater than 4.5 kg within past year; 3) oral or IV antibiotic use within the past 3 months; 4) regular use of aspirin or NSAIDs; 5) smoking; 6) known allergy to fish; 7) intention to relocate out of study area within next 4 months; 8) abnormal liver/kidney function as ascertained at a baseline blood draw.

Intervention: a) Placebo and b) Supplemental soluble fiber (35 g/d) + supplemental n-3 PUFA (6 g/d eicosapentaenoic acid (EPA) and docosahexaenoic acid (DHA).

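### The single-gene crossover model in section 9.b has no period term, and the sequence indicator cannot stand in for one

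*Combined protocol and SAP*

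**What the plan says.** Section 4 describes a two-order, two-period crossover: "Each treatment will be 30 days in duration with at least a 60-day washout period between treatments". It gives no allocation ratio or blocking for the two orders. The Synopsis plans "Recruitment of 40 participants with the goal of having 30 complete study measures".

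Section 9.b, Models (a), writes the single-gene and single-variable model as participant random effect plus intervention I plus sequence S plus error. On the remaining terms it says "Fixed effects will include an indicator, *I*, for intervention as well as demographic covariates (e.g., age, sex, BMI", to be included where appropriate. On sequence it says "models will include an indicator *S* of randomization sequence", offered in connection with differential carryover. Testing uses robust standard errors and Benjamini-Hochberg control of the false discovery rate.

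The only time terms appear later in 9.b, for the day 0, 15 and 30 data: "Terms for time and effect modification by intervention (time*intervention) will be added to this model if the data support autocorrelation". They index day within a period, depend on the data, and belong to the longitudinal analysis.

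Section 9.c bases single-gene power on a two-sided paired t-test with n=30 and alpha 0.05. It claims at least 80% for effect sizes above 0.5. That test has no period term either.

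**The concern.** In a two-period crossover, a change in level from period 1 to period 2 enters the active-minus-placebo difference with a plus sign in one sequence and a minus sign in the other. Only a period term, which varies within a person, can remove it. S, age and sex do not vary within a person, nor does BMI if taken at baseline.

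Some shift is plausible. The periods start at least 30 + 60 = 90 days apart in free-living people. The food frequency questionnaire is completed "over the 3 months prior to baseline to characterize habitual diets", so it would not record a later change in background diet.

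Two things are at stake: power for genes that have a shift, and, when the completing sequences are unequal, the estimates carried into the larger study that section 9.c says this pilot should inform. All genes share the one realised split, so the distortion does not average out across genes within the trial.

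**Working it through.** **Inputs.** From the documents: n=30 completers of 40 recruited, two-sided alpha 0.05, effect size 0.5 (Synopsis, 9.c), and the model terms (9.b). Assumed: the period shift δ, because no figure is given. Effects and δ are in SDs of the within-person difference, with one value per period. Tests are at an unadjusted 5%, as in 9.c, so the percentages are not the power of the planned FDR-controlled analysis.

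**The plan's own figure.** Normal approximation: 0.5 × √30 = 2.739; 2.739 − 1.960 = 0.779; power 78.2%, close to the stated 80%. The exact paired t-test on 29 df gives 75.4%, and 80% needs an effect of 0.53. Both 0.5 and 0.53 are used below.

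**What the written model estimates.** Let D be active minus placebo for one person and τ the true effect.

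- Placebo first (n1 people): E(D) = τ + δ
- Active first (n2 people): E(D) = τ − δ

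With complete data, participant + I + S estimates I by the plain mean of D:

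- Expected estimate = τ + δ(n1 − n2)/(n1 + n2). At 17/13 the bias is 4/30 = 13% of δ; at 18/12 it is 6/30 = 20%.
- Expected residual variance = 1 + 4·n1·n2·δ²/(n(n − 1)). At 15/15 and δ = 0.5 this is 1 + 7.5/29 = 1.26, so the standard error rises from √(1/30) = 0.183 to √(1.26/30) = 0.205.

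With a period term the estimate is the average of the two sequence means. Its standard error is ½√(1/n1 + 1/n2) on 28 df, and it does not depend on δ.

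**Power at 15/15 (exact calculation)**

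| Effect | δ=0.1 | δ=0.25 | δ=0.5 | δ=1.0 | With period term, any δ |
|---|---|---|---|---|---|
| 0.53 | 80% | 78% | 73% | 50% | 80% |
| 0.50 | 75% | 73% | 67% | 44% | 75% |

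**Unequal sequences, δ = 0.5, effect 0.53**

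| Placebo first / active first | Expected estimate without term | Power without | Power with |
|---|---|---|---|
| 17/13 | 0.53 + 0.07 = 0.60 | 83% | 79% |
| 13/17 | 0.53 − 0.07 = 0.46 | 60% | 79% |
| 18/12 | 0.53 + 0.10 = 0.63 | 87% | 78% |
| 12/18 | 0.53 − 0.10 = 0.43 | 53% | 78% |

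**How likely such splits are.** The allocation method is not stated, so two cases bracket it.

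| Split or worse | 20/20 randomised, 10 random dropouts | Simple randomisation |
|---|---|---|
| 17/13 | 27% | 58% |
| 18/12 | 6.5% | 36% |
| 20/10 | 0.04% | 9.9% |

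**Type I error without the term,** for shifts of 0.1 to 1.0: 2.1–4.9% at 17/13 and 4.6–5.3% at 18/12. It is clearly inflated only at splits such as 20/10 (10% at δ = 0.5, 17% at δ = 1).

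**Averaged over splits at δ = 0.5** (20/20, then simple randomisation): type I error 3.4% or 5.0%; power 72% or 71% without the term, 80% or 79% with it.

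**Checks on repeated-measures data.** Day-15 and day-30 values were simulated.

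- Mixed models at 18/12 with a 0.5 shift gave the same I with and without S, to within rounding (1e-15). Adding period moved the mean of I by 0.10 = 0.2 × 0.5.
- Robust standard errors (GEE) do not repair the loss. At 15/15 with δ = 1 and effect 0.5, the mean standard error was 0.253 against an empirical SD of 0.176, and power was 51% against 79% with the term.

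**The case against.** The strongest reply is that the harm depends on a shift the documents neither report nor imply. Entry is staggered, so season lines up only partly with period. Samples are described as stable at −80°C and the RNA-Seq assays are scheduled for Year 2, which argues against storage or assay timing as a main source. Individual drift is already in the within-person SD; only a common average shift matters. At 0.1 SD the loss at 15/15 is negligible, and at 0.25 SD it is about 2 points. This stands: the large losses need 0.5 SD or more.

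Several limits also stand. Genes without a shift lose nothing at 15/15. With unequal sequences power can rise as well as fall. The bias averages to zero if dropout is unrelated to sequence. This is a pilot, and the plan does not say that its single-gene estimates will size the next study.

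The longitudinal time-by-intervention model is a partial safeguard, because a shift that is constant within a period cancels from that interaction. But the terms are added only if the data support them, and they do not alter the main single-gene test. The general promise in 9.b to adjust for suitable covariates does not commit to a period term, and the written equation leaves it out.

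**Conclusion.** The concern holds. The single-gene model cannot absorb a period effect, and nothing else in the plan supplies the missing term. With equal completing sequences the cost is power: 0 to 2 points for shifts up to 0.25 SD, about 7 points at 0.5 SD and 30 points at 1 SD (effect 0.53, n=30, unadjusted 5%). With unequal sequences, 13% of the shift at 17/13 or 20% at 18/12 is added to or taken from the intervention estimate, conditionally on the realised split. This is not a general type I error problem. All sizes rest on an assumed shift; if the true shift is zero, no harm is done. The change is worth making before analysis because it costs little and protects against a shift of unknown size.

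**What to change.** Write the section 9.b model as y_ik = α_i + I_ik + P_ik + S_i + ε_ik, where P is a fixed indicator for period 1 or 2. Use it for every single-gene and butyrogenic-potential test, keeping I, S and the robust standard errors. For consistency, carry P as a covariate in the kernel association and gene-set null models and in the day 0/15/30 model. State the allocation ratio and any blocking, and report completers by sequence.

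Carryover is a separate question, which P does not answer. Residual effects can be checked with the period-2 day-0 stool samples and with the phospholipid values from "plasma collected on days 0 and 30", all already planned.

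The cost is one degree of freedom and no extra data. If there is no shift, power at effect 0.53 goes from 80.1% to 80.0% at 15/15, 79.3% at 17/13 and 78.4% at 18/12. Averaged over splits, the loss is about 0.5 point with 20/20 allocation or 1.5 points with simple randomisation.

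### The gene-level robust test has no stated small-sample correction or reference distribution, and its usual large-sample form would not hold a 5% false discovery rate with about 30 participants

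*Combined protocol and SAP*

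**What the plan says.** Section 9.b, Models a), plans for each gene "linear mixed models with a random effect for participant to account for the repeated measures of marker y", with fixed effects for intervention, randomization sequence and possible covariates. Errors "are assumed to be correlated within, and independent between, participants", so the participant is the cluster for a sandwich estimator. On inference the section says "Robust standard errors will be used to test for differential effect of intervention, and all p values will be corrected for multiple testing", the correction being made by "controlling the FDR using Benjamini-Hochberg".

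The synopsis gives the sample size: "Recruitment of 40 participants with the goal of having 30 complete study measures". Section 9.c bases single-gene power on a two-sided paired t-test at n=30 and alpha 0.05.

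For Aim 2, Section 9.b says "We will consider effects of butyrogenic potential (defined as above and below the median", which leaves about 15 participants in each half.

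The documents name no sandwich type, small-sample correction, reference distribution, degrees of freedom, FDR level for this trial or number of genes to be tested.

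**The concern.** A sandwich variance estimated from n participants is a noisy quantity. Its uncorrected form is biased low when n is small, and comparing the statistic with a normal distribution ignores the noise in the variance. At p = 0.05 the damage is slight and easy to overlook. Benjamini-Hochberg over a transcriptome works much further out. With 5,000 to 15,000 genes (an assumption), its first step is at 0.05/5,000 = 1e-5 to 0.05/15,000 = 3.3e-6. There the gap between a normal and a t distribution with 29 degrees of freedom is large.

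Exfoliome mRNA expression is the endpoint of both objectives in Section 3, and Section 9.c describes the study as a source of preliminary data for a larger one. A gene list with several times the stated share of false entries would carry those entries into that study.

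**Working it through.** **Inputs.** From the documents: n = 30 completers, 40 recruited (synopsis); participant-level clusters, robust standard errors and Benjamini-Hochberg (Section 9.b). Assumed: an FDR level of 5%, taken from the earlier lignan crossover study in Section 9.c, where "we detected differential expression of 32 genes between placebo and lignan extract (FDR<0.05) in exfoliated cells (n=42 participants"); 5,000 or 15,000 genes; 32 changed genes with a standardized effect of 1.0, or 5% or 10% of genes changed with an effect of 0.8; independent genes; normal within-person differences unless stated.

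**The plan's own figure.** Section 9.c claims at least 80% power for effects above 0.5. At d = 0.5 and n = 30 the noncentrality is 0.5 × √30 = 2.739. The exact paired t-test gives 75.4%; the normal approximation Φ(2.739 − 1.960) gives 78.2%. Exact 80% needs d = 0.53. This is a separate, minor gap. The plan gives no figure for realised FDR to reproduce.

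**Step 1: form of the statistic.** In a complete balanced crossover the intervention estimate is the mean within-person difference. With s² the sample variance of those differences, the uncorrected robust variance is ((n−1)/n) × s²/n. The statistic therefore equals t(n−1) × √(n/(n−1)). At n = 30 the standard error is low by a factor √(29/30) = 0.983, about 1.7%.

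**Step 2: true tail probability.** For nominal two-sided p with normal critical value z, the true probability is 2 × P(t(n−1) > z√((n−1)/n)). Example at p = 1e-4, n = 30: z = 3.891, 3.891 × 0.983 = 3.825, and 2 × P(t(29) > 3.825) = 6.4e-4, or 6.4 times nominal. Ratios of true to nominal:

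| Nominal p | n=30, uncorrected SE, normal | n=30, corrected SE, normal | n=30, uncorrected SE, t(29) | n=40, uncorrected SE, normal |
|---|---|---|---|---|
| 0.05 | 1.28 | 1.19 | 1.07 | 1.20 |
| 0.001 | 3.0 | 2.6 | 1.18 | 2.4 |
| 1e-4 | 6.4 | 5.4 | 1.23 | 4.4 |
| 1e-5 | 15.7 | 12.8 | 1.28 | 9.2 |
| 3.3e-6 | 25 | 20 | 1.31 | 13.6 |

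Columns two to four show the cause. Correcting the standard error but keeping the normal reference leaves most of the inflation; changing to t(29) removes nearly all of it.

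**Step 3: realised FDR.** Benjamini-Hochberg at 5% was simulated at n = 30 (60 to 200 runs per setting):

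| Genes | Changed (effect) | Uncorrected SE, normal | Uncorrected SE, t(29) | Corrected SE, t(29) |
|---|---|---|---|---|
| 5,000 | 32 (1.0) | 0.19 | 0.053 | 0.044 |
| 15,000 | 32 (1.0) | 0.29 | 0.061 | 0.051 |
| 5,000 | 250 (0.8) | 0.11 | 0.052 | 0.043 |
| 15,000 | 750 (0.8) | 0.11 | 0.057 | 0.048 |
| 5,000 | 500 (0.8) | 0.09 | 0.053 | 0.046 |
| 15,000 | 1,500 (0.8) | 0.09 | 0.050 | 0.044 |

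The excess is largest when few genes change, because the cutoff then stays in the far tail. With about 1,547 of 15,000 genes called, it moves in to about 0.05 × 1,547/15,000 = 0.005. If no gene responds, the chance of at least one false call is about 0.60 (5,000 genes) to 0.76 (15,000), against 0.045 and 0.085 with the corrected version (standard error of the last about 0.02). If all 40 are analysed, the uncorrected normal version gives an FDR of about 0.08 to 0.20.

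**Step 4: does the correction hold in the planned model?** The random-intercept model was simulated with sequence, covariates, 17:13 allocation and missing visits. CR2 with a t reference gave ratios of 0.90 to 1.16 from p = 0.05 to 1e-5, within simulation error of 1. Degrees of freedom were 29 with complete data and about 27 with 15% of samples missing.

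**Step 5: Aim 2.** At nominal 1e-4, an uncorrected test with a normal reference inside one half (n = 15) has a true probability of 2 × P(t(14) > 3.891 × √(14/15)) = 2.1e-3, or 21 times nominal. A contrast of the two halves (15 against 15) gives 2 × P(t(28) > 3.891 × √(14/15)) = 8.0e-4, or 8 times.

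**The case against.** A reader might infer that the planned gene list will fail to hold its FDR. The documents do not support that. Section 9.b leaves the sandwich type and the reference distribution open, and the only distribution named for single-gene work is a t, in the power statement of Section 9.c. An analyst who used an uncorrected standard error with t(29) would still comply with the text and would obtain an FDR of about 5% to 6%. This stands, and it makes the point conditional.

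A reader might also infer that robust standard errors are the wrong choice. That does not follow either. The standard error is only about 1.7% low, and a robust variance protects against correlation between samples in the same period that a random intercept does not capture.

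The size is uncertain too. Gene count, FDR level, share of changed genes and effect sizes are assumptions, and the figures for no responding gene are an extreme case. The kernel and gene-set pathway tests are not shown to be affected. For Aim 2 the plan says only that effects will be considered, so the 15-per-half tests are one way of carrying it out.

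What remains is that two analysts could both follow Section 9.b and report lists whose false share is about 5% in one case and up to 29% in the other.

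**Conclusion.** The point holds as a conditional one. The plan leaves unstated a choice that decides whether its FDR is held, and the usual large-sample version of the stated method does not hold it. With an uncorrected sandwich and a normal reference, a nominal 5% FDR becomes about 9% to 29% at n = 30. The cause is mainly the normal reference in the far tail.

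The tail ratios are exact for normal within-person differences in complete balanced data. The FDR range also depends on the assumed gene numbers and effects and on independence between genes. Heavy-tailed differences (t with 5 degrees of freedom, 15,000 genes) gave similar results with some genes changed: 0.08 to 0.21 for the uncorrected normal version and 0.03 to 0.04 for the corrected one. Strongly one-sided skew (exponential differences) broke every version, including the corrected one (0.16 to 0.74).

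**What to change.** Replace the inference sentence in Section 9.b with: *Intervention effects will be tested with bias-reduced (CR2) participant-clustered standard errors and a t reference with Satterthwaite (participant-level) degrees of freedom, or with a t test on within-participant differences of period summaries; p values will not be taken from the normal distribution.* Use the same method for any gene-level test by butyrogenic potential. State the FDR level for this trial and the rule that decides which genes are tested.

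Kenward-Roger inference is not an equivalent substitute. It is model-based and, under a random intercept with repeated samples per period, ignores extra within-period correlation. In a simulation with n = 30 and two samples per period, an assumed extra correlation of 0.20 gave about 5.5 times nominal at 1e-4. A permutation check without a pass rule would not define an FDR procedure and is not needed here.

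The cost is one sentence, a software option and fewer calls. With 32 changed genes of 15,000, true calls fall from about 30.4 (42.98 − 12.61) to 25.9 (27.41 − 1.46), while false calls fall from about 12.6 to 1.5. Because the fix is accurate only for roughly symmetric within-person differences, the plan should also name a suitable transformed scale for expression.
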